1. BACKGROUND AND SIGNIFICANCE

As concerns regarding the effects of agriculture on human and environmental health mount^{1,2}, a growing number of farmers are seeking ways to improve health from the ground up. A promising way by which a growing number farmers are seeking to improve environmental health is by using agro-ecological practices (i.e., farming more closely in harmony with natural systems), which include practices such as multi-cropping, ley rotations, and/or integrated crop-livestock systems³. When properly implemented, agro-ecological practices can improve soil health, nutrient cycling, and biodiversity above and below ground³⁻⁵. Despite potential major ecological benefits, we lack critical knowledge if consuming foods from agro-ecological systems also benefits human health. The purpose of this project is to test the hypothesis that consuming foods produced using agro-ecological practices improves consumer health compared to consuming similar foods from conventional (monoculture) farming systems.

This work will utilize a randomized cross-over design to compare an agroecological vs conventional sourced diet, and determine their effects on inflammation and cardio metabolic health signatures in middle-aged adults (35-60 y old). Diets will be isocaloric and matched for macronutrient content, and consumed for 44 days each with a 14-day washout (habitual diet) period in between. Blood, urine, and stool samples will be obtained before and after the dietary interventions, in addition to data about physical activity and questionnaires regarding quality of life.

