3.3 Study Schedule

ACTIVITY/VISIT	WEEK	DURATION
PHONE SCREEN A scripted phone screen will be performed to determine pre-eligibility prior to consent.	1	15 min
CONSENT A one-on-one consent visit will be conducted privately with staff either in-person or via Zoom.	1	1 h
SCREENING This visit will take place in the morning after an overnight fast and will have the following procedures: informed consent, screening blood draw (including serum pregnancy test for women of child-bearing potential), health history, height and weight, and screening questionnaires regarding food intake, health, and sleep.	1	2 h
BASELINE VISIT DIET 1 This visit will take place in the morning after an overnight fast. Participants will be asked to complete a fasted blood draw and questionnaires, and bring in urine and stool samples that were collected using at-home collection kits.	2	1 h
INTERVENTION DIET 1 Participants will be randomized to consume one of the following sourced diets: agroecological or conventional. They will follow this nutrition pattern for 44 days. During this time, participants will come to the NDFS building twice a week to pick up food.	2-8	1 h per week
POST VISIT DIET 1 On the last day of diet 1, participants will be asked to complete a fasted blood draw and questionnaires, and bring in urine and stool samples that were collected using at-home collection kits.	8	1 h
WASHOUT PERIOD Participants will consume self-selected (habitual) diets for 14 days. No involvement from research team.	9-10	none
BASELINE VISIT DIET 2 This visit will take place in the morning and will have a fasted blood draw. Participants are also asked to bring in stool and urine samples that were collected using at-home collection kits.	10	1 h
INTERVENTION DIET 2 Participants will now start their second nutritional intervention (agroecological or conventional sourced diet depending on the diet consumed during the first intervention). During this time, participants will come to the NDFS building twice a week to pick up food.	10-16	1 h per week

POST VISIT DIET 2 On the last day of diet 2, participants will be asked to complete a fasted blood draw and questionnaires, and bring in urine and stool samples that were collected using at-home collection kits.	16	1 h
---	----	-----

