- **Blood Draw**: A trained phlebotomist (the PI) will draw a fasted blood sample for metabolomics and inflammatory biomarker assays. A total of 15 mL of blood (1 TBPS) will be drawn. Our plans for measuring cytokines and metabolites are discussed in the *Analytical Procedures and Statistical Considerations subsection* (see below).

Intervention (44 days x 2 diets; 1 hour per week): After completing all baseline testing, participants will be randomized to one of the two starting diets (agroecological or conventional, for 44 days with a 14 day washout period until they start their second diet (agroecological or conventional depending on the starting diet). In accordance with established protocols, a research dietitian will provide weight-maintenance diets with a macronutrient distribution of 20% protein, 30% fat, and 50% carbohydrate based on each individual's daily energy requirement (Harris-Benedict equation). All foods that participants consume during those 4-weeks will be provided by the Metabolic Kitchen at NDFS, and dietitian-led group classes and handouts with food preparation instructions will be provided to the participants to ensure compliance. The diets will be provided as 4-day rotating menus and participants will be asked to pick-up food twice weekly at the NDFS building. This will allow the research time to interact face-to-face with the participant, address any issues, and further ensure compliance. All subjects assigned to the same diet will receive identical meals and snacks, but portion sizes will be determined based on the previously mentioned daily energy requirement. Food for the agroecological diet will be sourced predominantly from the Greenacres farm (Cincinnati, OH) and food for the conventional diet

will be sourced from local grocery stores (non-organic produce). All foods will be stored in food-grade fridges and freezers in the CHNS Metabolic Kitchen and food boxes will be prepared weekly by staff. Examples of the diets are presented in **Table 2**.

Table 2: Examples of Meals

Breakfast	Whole milk, eggs, oatmeal, and blueberries
Snack	Rice cakes
Lunch	Ground beef, tomato salad and cherries
Snack	Apple with nut butter
Dinner	Grilled chicken with rice and steamed broccoli

Additionally, subjects will complete the following study procedures during each intervention period:

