4.2 Compensation

Participants will receive a maximum compensation of \$1000. This is a fair amount, in our opinion, as meals and snacks are provided to participants. Participants will thus save on groceries by participating in this study. Participants will receive \$25 for the screening visit; however, no compensation will be provided for those who only participate in the consent portion of the screening visit. Participants will receive another \$975 after they complete both dietary interventions. Participants will be paid in full at the end of the study. If a participant drops out of the study before completing all two diet intervention periods they will be paid according to the degree of completion if only one diet is completed. No compensation other than the \$25 for the screening is provided if participants drop out in the first week of the first diet intervention.

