7. ANALYTICAL PROCEDURES AND STATISTICAL CONSIDERATIONS

- **Inflammation:** Inflammatory biomarkers (IL-6, VCAM-1, TNF-alpha and C-reactive protein [CRP]) will be measured using ELISA kits at Dr. [name]'s laboratory at Utah State University. Plasma samples will be stored at -80°C until cytokine analyses are performed.
- **Dietary logs:** The Diet History Questionnaire III (NIH) and 7-day food records will be analyzed by dietetic staff within Dr. [name]'s laboratory at Utah State University.
- **Metabolomics:** Mass spectrometry techniques will be used for untargeted and/or targeted assessment of blood and/or urinary metabolites. This analysis will give insight into the appearance of food-derived metabolites in the human body and how they may impact biomarkers of human health. This analysis will be performed using de-identified samples by Metabolon Inc (a company dedicated to metabolomics analysis) and/or the Plants for Human Health Institute. Samples will be provided to these core services as de-identified samples. No other data will be shared with these core services. Plasma and urine samples will be stored at -80°C until metabolomics analyses are performed.
- **Gut microbiome taxonomy:** DNA will be extracted from stool samples using a QIAamp Fast DNA Stool Mini Kit following manufacturer's instructions and analyzed for taxonomic assignment using 16s rRNA sequencing at Utah State University's Genomics Core. Samples will be provided to the core service as de-identified samples. No other data will be shared with the core service.

- **Statistical analysis:** Change scores (post-dietary intervention – baseline) will be created for all inflammatory biomarkers and metabolites. Metabolic intermediate data will be reduced into Metabolic Factors using Principal Component Analysis (PCA) of the change scores. Factor scores will be computed for each individual for both diets. Change scores and factor (change) scores for both diets will be compared using paired t-tests. $P < 0.05$ will be considered statistically significant and analyses will be performed in SAS 9.4 (SAS, Cary, NC).

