- **Power Calculations:** Using untargeted metabolomics for our power calculations of the number of participants we need to recruit, we assume a P -value ≤ 0.05 , Q -value ≤ 0.3 , and standard deviation of 0.3 based on previous work^{7,8}. 600 metabolites are typically identified and a conservative estimation in longer-term dietary intervention trials is that 40-80 metabolites will be significantly different with a mean of 0.157 (18 % difference). An $n=34$ per group is expected to provide true discovery rates ranging from 89-93 % assuming differences in 40-80 metabolites. Assuming a drop-out of 25%, the final number of participants we anticipate to recruit is $N=40$.

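### The paired t-test discards the diet-1 change scores of people who finish one diet and leave; the main cost is precision, and bias is possible only under specific withdrawal patterns

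*Combined protocol and SAP*

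**What the plan says.** The trial is a two-diet randomised cross-over (Section 1). Section 7 defines the outcome variable: "Change scores (post-dietary intervention – baseline) will be created for all inflammatory biomarkers and metabolites". Metabolites are reduced to factors by principal component analysis of the change scores. The only diet comparison is then: "Change scores and factor (change) scores for both diets will be compared using paired t-tests".

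A diet-1 change score needs samples at two visits, and both are planned for everyone. At Baseline Visit 1 the phlebotomist "will draw a fasted blood sample for metabolomics and inflammatory biomarker assays" (Section 3.4). At the other end, "On the last day of diet 1, participants will be asked to complete a fasted blood draw and questionnaires" (Section 3.3). Urine and stool are brought to the same visits.

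The protocol expects withdrawal. Section 4.2 says of people who drop out that "they will be paid according to the degree of completion if only one diet is completed". The power paragraph of Section 7 reads "Assuming a drop-out of 25%, the final number of participants we anticipate to recruit is" 40. Section 4.1 sets a goal of at least 18 completers from up to 40 enrolled. The document gives no analysis population, missing-data method, mixed model or sensitivity analysis for withdrawal.

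**The concern.** A paired t-test works on within-person differences. Someone with a change score on one diet only has no difference, so the planned test drops that person. Including the person in the principal component analysis would not help, because the factor scores go to the same paired test.

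Two things are at stake. First, randomised data that were collected, and partly paid for, contribute nothing to the estimate. Second, the estimate rests on people who chose to go on to a second diet. That choice is made after randomisation by people who have experienced one diet, so it could differ by starting diet. Adding a period term to a model fitted to completers would not cure either problem; what matters is who is analysed.

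**Working it through.** **Numbers of completers.** The plan's recruitment figure cannot be reproduced: 34/(1 - 0.25) = 45.3, so 46, not 40. Taking 40 recruited and 25% drop-out as stated leaves 40 x 0.75 = 30 completers. I use 30, and also 18 (Section 4.1).

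**Assumptions not in the documents.** The correlation rho between a person's two change scores is taken as 0 to 0.8. The number k who leave after finishing diet 1 is varied. Change-score variance is 1 on each diet, sequences are of equal size, and rho is treated as known.

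**Precision.** For starting diet s = +1 or -1, write the period-1 change as mu + pi/2 + s·d/2 and the period-2 change as mu - pi/2 - s·d/2, where d is the diet difference and pi the period effect. With balanced sequences, the information on d is 1/[2(1 - rho)] from each completer and 1/4 from each diet-1-only person. With c completers:

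- paired test: variance = 2(1 - rho)/c
- all available data: variance = 1/{c/[2(1 - rho)] + k/4}
- ratio = 1/[1 + k(1 - rho)/(2c)]

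Example: c = 30, k = 10, rho = 0 gives 1/(1 + 10/60) = 0.857, a cut of 14.3%. It equals having c + k(1 - rho)/2 = 35 completers.

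| c | k | rho 0 | rho 0.5 | rho 0.8 |
|---|---|---|---|---|
| 30 | 2 | 3.2% | 1.6% | 0.7% |
| 30 | 6 | 9.1% | 4.8% | 2.0% |
| 30 | 10 | 14.3% | 7.7% | 3.2% |
| 18 | 10 | 21.7% | 12.2% | 5.3% |
| 18 | 22 | 37.9% | 23.4% | 10.9% |

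Entries are cuts in variance. On the standard-error scale, the row with 30 and 10 is 7.4%, 3.9% and 1.6%.

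**Bias, with no true diet effect.** For starting diets 1 and 2, let q1 and q2 be the proportions leaving after diet 1, and C1 and C2 the covariances between leaving and the diet-1 change. In a sequence with values q and C, the stayers' mean diet-1 change is -C/(1 - q) and their mean diet-2 change is rho times that. Pooling the completers:

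- from response-related leaving: size of bias = (1 - rho)·|C1 - C2| / [(1 - q1) + (1 - q2)]
- from a period effect pi: size of bias = pi·|q1 - q2| / [(1 - q1) + (1 - q2)]

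With leaving more likely by log-odds 1 per SD of the diet-1 change, numerical integration gives C = 0.139, 0.177 and 0.199 at q = 0.20, 0.30 and 0.40. In SD of change:

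- Same dependence and same rate in both sequences: C1 = C2, bias 0.
- 40% v 10%, unrelated to response, no period effect: bias 0.
- 30% v 20%, same dependence: (0.177 - 0.139)/1.5 = 0.025 at rho 0 and 0.013 at rho 0.5.
- 40% v 10%, unrelated to response, period effect 0.3 SD: 0.3 x 0.3/1.5 = 0.06.
- 40% response-related v 10% random: 0.199/1.5 = 0.13 at rho 0, 0.09 at rho 0.3 and 0.07 at rho 0.5.

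In the last case, simulating 40 participants (20,000 runs) gave paired-test false-positive rates of 8.3%, 6.8% and 6.7% at rho 0, 0.3 and 0.5, against 5% nominal. A 1,500-run simulation gave 8.7%, 6.6% and 7.3%. In the latter, generalised least squares keeping the diet-1 data had bias 0.000, -0.005 and 0.001. That estimator uses known variances; the false-positive rate of a fitted mixed model was not simulated.

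**The case against.** A reader might infer that the completer comparison is biased whenever leaving depends on how a person fared on diet 1. That is not so. If the dependence and the rate of loss are the same in both sequences, the selection effects cancel.

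Nor do the documents suggest that the worst pattern is likely. The diets are isocaloric, matched for macronutrients and differ by food source (Sections 1 and 3.4). The endpoints are assayed from stored samples, so participants are unlikely to know their change in them. A worse change has no defined direction for untargeted metabolites or factors. Payment of $975 follows completion of both diets, which discourages leaving midway. An indirect link through tolerability is conceivable, since Section 5 mentions gastrointestinal discomfort from dietary change, but nothing shows that it would differ by diet. All this stands, and it makes bias a secondary argument.

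It can also be said that the precision gain is small, that some leavers will go before finishing diet 1 (Section 4.2 mentions the first week), and that over-enrolment already allows for attrition. The first two are right for high rho or few diet-1-only people, as the table shows. Over-enrolment protects precision only in part: 30 completers is below the plan's own 34, and it does nothing about selection.

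Finally, a standard cross-over mixed model would retain these people by default. True, but the plan does not specify one, and a version restricted to completers would keep the problem.

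**Conclusion.** The point holds as a modest, cheaply corrected weakness. The planned test discards randomised diet-1 data that the protocol collects. At 30 completers the avoidable variance is about 2-14% with 6 to 10 diet-1-only people, and about 1-3% with 2. At 18 completers with 10 to 22 such people it is about 5-38%. The low end of each range is for rho 0.8 and the high end for rho 0. The documents give neither rho nor the timing of withdrawal, and the counts of 10 leavers and 30 completers are arithmetic from 40 and 25%, not figures the plan states.

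Bias is conditional. It ranges from 0 under symmetric withdrawal, through 0.01-0.03 SD at 30% v 20% loss, to 0.07-0.13 SD (rho 0.5 to 0) in a near-worst case, where the false-positive rate is about 7-9%. The documents do not support saying that bias will occur.

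**What to change.** In Section 7, replace the paired t-test as the main analysis with a linear mixed model for each biomarker, metabolite and factor change score: fixed diet and period, random participant, with small-sample degrees of freedom such as Kenward-Roger. PROC MIXED in the SAS package already named will fit it. State that the analysis includes every randomised participant with a change score on at least one diet, and that their available change scores also enter the principal component analysis. Keep the paired t-test on completers as a sensitivity analysis, and report withdrawals by starting diet and period.

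The cost is a paragraph of SAP text, a short program, and assays at two time points on samples from a few one-diet completers. No visit or eligibility rule changes. The result will rely on withdrawal being explained by observed data and on the random-effect model (equal variances and a common correlation across diets), so the comparison with the completer analysis should be shown.

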4. SUBJECT RECRUITMENT AND COMPENSATION

4.1 Recruitment

Subjects will be recruited by posting flyers in designated areas around USU's campus, and through advertisement on public Facebook pages (Cache Valley Classifieds and/or Marketplace), local NextDoor pages, Craigslist, Reddit (R/Logan), Instagram, and/or Twitter. In the advertisement, potential subjects for this study will be directed to contact the study team by email or phone to obtain more information about the study, if interested. Participants who are interested will be provided with a copy of the informed consent by email. When the participant expresses interest in being in the study, the study team member will confirm, by telephone, that the participant meets most of the inclusion/exclusion criteria (ones that can be determined without the need for a blood draw) before scheduling him/her for a consent meeting. Subjects will attend a one-on-one information/consent session that will be conducted by a trained member to present the details of the study. We anticipate that we will need to telephone screen approximately 150 people and that approximately 30 will be consented. We will enroll up to 40 participants to meet our goal of having at least 18 participants complete the study.

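### The analysis declares metabolites at P<0.05 alone, although the trial is sized on P≤0.05 and Q≤0.3, and over most of the assumed range the resulting list would break that Q limit

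*Combined protocol and SAP*

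**What the plan says.** Both statements are in section 7, in adjacent paragraphs.

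- **Statistical analysis.** Change scores "will be created for all inflammatory biomarkers and metabolites". Metabolite data are also reduced to principal-component factors. Then "Change scores and factor (change) scores for both diets will be compared using paired t-tests", and "P < 0.05$ will be considered statistically significant".
- **Power Calculations.** Discoveries are required to satisfy P≤0.05 together with "Q -value ≤ 0.3 , and standard deviation of 0.3 based on previous work". The paragraph adds that "600 metabolites are typically identified and a conservative estimation in longer-term dietary intervention trials is that 40-80 metabolites will be significantly different", with a mean difference of 0.157. It gives n=34 per group, a true discovery rate of 89–93%, drop-out of 25% and recruitment of 40.
- **Metabolomics.** The platform is left open: "untargeted and/or targeted assessment of blood and/or urinary metabolites".
- **Section 4.1, Recruitment.** "We will enroll up to 40 participants to meet our goal of having at least 18 participants complete the study".

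The Q-value appears only in the power paragraph. No other section gives a false discovery or multiplicity rule.

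**The concern.** The trial is sized under one decision rule and analysed under another. The power paragraph limits the expected share of false discoveries to 0.3; the analysis paragraph has no such limit. The principal-component step does not supply one, because factor scores are tested in addition to the individual change scores.

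Metabolites are objective 2 and the only basis for the sample size. With several hundred tests at 5%, the number of false positives is of the same order as the number of true differences the plan expects. Readers would see a list of significant metabolites without knowing that it may fail the standard on which the trial was justified.

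**Working it through.** **Inputs from section 7, Power Calculations.** 600 metabolites; m = 40 to 80 truly different; mean difference 0.157; SD 0.3; P≤0.05; Q≤0.3; n=34. Recruitment of 40 less 25% leaves 40 × 0.75 = 30. Section 4.1 gives a floor of 18 completers.

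**Assumptions.** Tests are two-sided. SD 0.3 is that of the paired difference (the plan does not say). Every true difference equals 0.157.

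**The plan's own figure.** The standardised difference is 0.157/0.3 = 0.523. Noncentral-t power at n=34 is 84.2%, or 72–83% for m = 40–80 once Benjamini-Hochberg Q≤0.3 is added. The stated 89–93% is therefore not reproduced as power. Read as one minus the false share at P<0.05, the result is 55–72%, which also misses it. A one-sided paired test gives 91.0% but does not vary with m. The check below does not rely on the 89–93%.

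**Formulas for the rule as written.** Let π be the power per true difference.

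- Expected false positives: FP = 0.05 × (600 − m)
- Expected true positives: TP = π × m
- False share = FP / (FP + TP)

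Example, n=30 and m=40: FP = 0.05 × 560 = 28.0; TP = 0.791 × 40 = 31.6; share = 28.0/59.6 = 47%.

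| n | π | m=40 | m=60 | m=80 |
|---|---|---|---|---|
| 34 | 0.842 | 45% | 35% | 28% |
| 30 | 0.791 | 47% | 36% | 29% |
| 18 | 0.553 | 56% | 45% | 37% |

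Simulation with independent metabolites agrees: at m=40, 45% (n=34) and 46% (n=30); at m=80, 28% and 29%.

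**Where the share equals 0.3.** Setting 0.7 × 0.05 × (600 − m) = 0.3 × π × m gives m = 21 / (0.035 + 0.3π).

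- n=34: 73.0, so 74 or more are needed.
- n=30: 77.1, so 78 or more.
- n=18: 104.5, outside the assumed range.

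**Sensitivity.**

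- *Perfect power (π=1), which removes both SD and n:* the share is 28/68 = 41% at m=40 and 26/106 = 25% at m=80. The crossing is 21/0.335 = 62.7, so 63 or more are needed.
- *The stated 89–93% taken as power:* the crossings are 69.5 and 66.9, so 70 and 67.
- *SD 0.3 read as a two-group SD, n=34 per group:* π = 0.566, the share runs from 55% to 36%, and the crossing is 102.5. The limit is exceeded throughout.
- *True effects varying around 0.157 (assumed SD 0.03 to 0.08):* the crossing rises to about 76–84 at n=34 and 80–87 at n=30.
- *No metabolite differs:* 0.05 × 600 = 30 are declared on average. A targeted panel of 100 would give 5; testing both plasma and urine would give more than one panel alone.

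The false share depends on the proportion truly different (40/600 = 6.7% to 80/600 = 13.3%), not on panel size.

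**The same data with P<0.05 and Benjamini-Hochberg Q≤0.3** (simulation, independent metabolites):

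| n | m | P<0.05 only: true / false | With Q≤0.3: true / false | False share with Q |
|---|---|---|---|---|
| 34 | 40 | 34 / 28 | 29 / 12 | 28% |
| 34 | 80 | 67 / 26 | 66 / 24 | 26% |
| 30 | 40 | 32 / 28 | 26 / 11 | 28% |
| 30 | 80 | 63 / 26 | 61 / 22 | 26% |
| 18 | 40 | 22 / 28 | 10 / 5 | 28% |
| 18 | 80 | 44 / 26 | 33 / 12 | 26% |

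With no true differences at n=30, the average declared falls from 30 to about 0.6.

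**The case against.** The sponsor may have meant the Q-value to apply. The P<0.05 sentence is generic, covering inflammatory markers, factors and metabolites alike, and the Q limit stands in the next paragraph. The factor scores could be the main metabolic inference, and objective 2 is framed as insight into pathways. At 80 true differences the remedy moves the false share only from 29% to 26% at n=30. The figures of 74 and 78 rest on equal effects and on one reading of the SD, and the plan's 89–93% could not be matched, so its sizing model is not fully known. The 18 completers are a minimum, so that row is a worst case.

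Some of this stands. The lack of adjustment is inferred from silence, the exact crossings depend on the model, and the rule as written does meet the limit near the top of the range if the paired reading is right. None of it removes the mismatch. The written text tests individual metabolites and names P<0.05 alone. Unequal effects and the two-group SD both make the false share worse, and the 63 threshold needs neither SD nor n. If a Q rule was intended, the sentence is still missing.

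The remedy also has limits. Benjamini-Hochberg controls the average false share: at n=30 with 40 true differences, about 4 in 10 simulated trials still exceeded 0.3. With no true differences, there remains roughly a 30% chance of declaring at least one metabolite.

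**Conclusion.** The concern holds. At P<0.05 alone, the expected false share exceeds the plan's 0.3 limit unless at least 74 (n=34) or 78 (n=30) of 600 metabolites truly differ. This assumes two-sided paired tests, a paired SD of 0.3 and equal effects of 0.157. The firmer statement is that below 63 true differences the limit is exceeded whatever the SD or sample size, and that covers more than half of the assumed 40–80 range. At the floor of 18 completers, or if 0.3 is a two-group SD, it is exceeded across the whole range. This should be fixed before analysis; it affects how the metabolite results can be read.

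**What to change.** Add to the Statistical analysis paragraph that a metabolite is declared different only if P<0.05 and its Benjamini-Hochberg Q-value, computed over all metabolites tested, is at or below the 0.3 used for sizing. Report Q-values beside P-values. The plan names neither a Q-value method nor the set of tests it covers, so the sentence must settle both. The Power Calculations paragraph should also say whether SD 0.3 refers to the paired difference.

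The cost is one sentence and one SAS procedure call, with no new data. The price in true findings is small when many metabolites differ (63 to 61 at n=30 with 80 true) and moderate when few do (32 to 26 with 40 true). It is large at 18 completers (22 to 10 with 40 true). The list would still carry about 26–28% false discoveries on average, which is what the plan's own limit allows.

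### The 89-93% true discovery rates quoted at n=34 per group cannot be reproduced from the inputs stated with them, either as average power or as 1 - FDR

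*Combined protocol and SAP*

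**What the plan says.** The Power Calculations paragraph in section 7 is the only justification given for the sample size. It takes P≤0.05, "Q -value ≤ 0.3 , and standard deviation of 0.3 based on previous work", and 600 metabolites, of which "40-80 metabolites will be significantly different with a mean of 0.157 (18 % difference". It then says that n=34 per group "is expected to provide true discovery rates ranging from 89-93 % assuming differences in 40-80 metabolites". The next sentence reads "Assuming a drop-out of 25%, the final number of participants we anticipate to recruit is" 40.

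Three other places bear on this:

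- Section 1 fixes the design: "This work will utilize a randomized cross-over design to compare an agroecological vs conventional sourced diet".
- The Statistical analysis paragraph of section 7 fixes the test: "Change scores and factor (change) scores for both diets will be compared using paired t-tests". Its only decision rule is that P<0.05 "will be considered statistically significant and analyses will be performed in SAS 9.4". It mentions no Q-value.
- Section 4.1 enrols up to 40 "to meet our goal of having at least 18 participants complete the study".

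The plan does not define true discovery rate. Nor does it state sidedness, the measurement scale, what the SD of 0.3 describes, any within-person correlation, or the formula or software.

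**The concern.** A true discovery rate can mean two things: the share of truly different metabolites that are detected (average power), or the share of called metabolites that truly differ (1 - FDR). Average power is the likelier meaning, because with a Q cut-off it varies with the number of true differences, as the stated range does. But 1 - FDR is the more literal sense of the words, and the two lead to different expectations.

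If neither reading yields 89-93%, the sample size rests on a figure that nobody can check. A reader who takes it as 1 - FDR would expect 7-11% of called metabolites to be false, although the plan itself tolerates a Q-value of up to 0.3. A reader who takes it as power cannot tell what power the trial has at the number likely to finish. The wording *per group* adds doubt, since in a crossover each completer supplies both diets.

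**Working it through.** **Inputs.** From Power Calculations: m = 600; m1 = 40 or 80 true differences, so m0 = 560 or 520; d = 0.157; SD 0.3; n = 34; P≤0.05; Q≤0.3. From Statistical analysis: paired t-test. Assumed here, because not stated: independent tests; two-sided unless noted; 0.3 as the SD of the within-person contrast unless noted. Result pairs are for m1 = 40 / 80.

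**Formulas.** With power π(α) from the noncentral t:

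- Paired noncentrality: d√n / SD = 0.157 × √34 / 0.3 = 3.05.
- Two independent groups of 34: 0.157 / (0.3 × √(2/34)) = 2.16.
- α is the smaller of 0.05 and the level at which m0·α / (m0·α + m1·π(α)) = 0.3.
- 1 - FDR = m1·π / (m1·π + m0·α).

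**Step 1. The plan's figure as 1 - FDR.** P≤0.05 alone lets through 560 × 0.05 = 28 or 520 × 0.05 = 26 false positives. Even at perfect power, 1 - FDR is at most 40/68 = 58.8% or 80/106 = 75.5%. Adding Q≤0.3 raises the lower figure to 70.0% and leaves the upper at 75.5%. At n=34 (paired, two-sided):

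- m1 = 40: α = 0.0227, π = 0.743. False 560 × 0.0227 = 12.7, true 40 × 0.743 = 29.7, so 1 - FDR = 29.7/42.4 = 70.0%.
- m1 = 80: the Q rule alone would allow 0.0564, so P≤0.05 binds and π = 0.842. False 26, true 67.3, so 1 - FDR = 67.3/93.3 = 72.1%.

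The formula is a ratio of expectations. A simulation of 2,000 runs (Benjamini-Hochberg with P≤0.05) gave 71.9 / 73.9% at n=34 and 71.9 / 75.8% at perfect power. About 75% is therefore an approximate ceiling, well short of 89-93%.

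**Step 2. The plan's figure as average power, both cut-offs, n=34, d = 0.157, SD 0.3.**

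| Test | Power, m1 = 40 / 80 |
|---|---|
| Paired, two-sided, t | 74.3 / 84.2% |
| Paired, two-sided, normal approximation | 78.7 / 86.2% |
| Paired, one-sided, t | 84.6 / 91.0% |
| Two independent groups of 34, two-sided, t | 31.3 / 49.3% |

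The closest misses that keep 0.157 and 0.3 are one-sided and paired. With Q≤0.3 alone and the normal approximation, power is 86.8 / 93.5%. With P≤0.05 alone it is 91.0% (t) or 92.0% (normal), inside the range but a single value that does not vary with m1.

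**Step 3. What comes close (paired, t, both cut-offs, n=34).**

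| Change to the inputs | Power, m1 = 40 / 80 |
|---|---|
| d = 0.18, two-sided | 87.5 / 92.4% |
| d = ln(1.18) = 0.166, one-sided | 88.5 / 93.4% |
| 0.3 as per-diet SD, correlation 0.63: contrast SD 0.3 × √(2 × 0.37) = 0.258, two-sided | 88.6 / 93.1% |

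The first two replace the stated mean; the third adds a correlation that the plan does not give. On the natural-log scale exp(0.157) = 1.170, a 17.0% difference, so 0.157 and 18% do not agree there.

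**Step 4. At the numbers the plan may reach.** 40 × 0.75 = 30 completers, not 34. Two-sided paired t, both cut-offs:

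| Completers | Contrast SD 0.3 | Per-diet SD 0.3, assumed correlation 0.7 (contrast SD 0.232) |
|---|---|---|
| 30 | 65.9 / 79.1% | 91.1 / 94.7% |
| 18 | 25.1 / 46.1% | 61.0 / 77.1% |

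With contrast SD 0.3, 1 - FDR is 70.0 / 70.9% at 30 completers.

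**The case against.** The strongest reply is that the power half shows missing specification, not a proven miscalculation. Sidedness, scale, SD type and formula are all unstated, so 74-84% reflects choices made here; the normal approximation alone moves it to 79-86%. The 18% is printed beside 0.157, and putting 0.18 on the scale of the SD roughly recovers the stated range. The two-group figure of 31-49% also assumes that 0.157 and 0.3 share a scale: if the 18% were on log2 (0.239), two groups of 34 would give about 84-90%. The SD is attributed to cited work that cannot be checked here.

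Most of this stands, and it limits what can be said. A reader might infer that the authors made an arithmetic slip, that they sized the trial as two parallel groups, or that the trial is underpowered. The documents support none of these. An unstated but reasonable within-person correlation would bring the power to the quoted level or above it.

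The reply does not rescue the figure as written. No variant tried with 0.157 and 0.3 as stated matched both ends of 89-93%. Under independent tests, the 1 - FDR result does not depend on the SD, the effect, the pairing or the sidedness.

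**Conclusion.** The concern holds as a failure of reproducibility. Stated: 89-93%. As 1 - FDR: about 70-75% under both cut-offs at any n, or at most about 59-75% under P<0.05 alone, assuming independent tests. As average power at n=34 with contrast SD 0.3: 74-84% two-sided, 85-91% one-sided.

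The cause may be the unreconciled pair of 0.157 and 18%, or an assumption left out of the text; the documents do not settle which. The direction of correction is likewise open: at 30 completers, two-sided power is 66-79% or 91-95%, depending on what the SD of 0.3 means and on a correlation that is assumed here. The 1 - FDR reading is less likely to be what was meant, but a reader who adopts it would expect 7-11% false findings where the cut-offs imply about 25-30%.

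This should be fixed, because it is the sole basis for the sample size and is quoted at 34 when the plan's own dropout leaves 30.

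**What to change.** Rerun the calculation for the paired crossover test at 30 completers, show it also at 18, and replace the sentence. Report average power and 1 - FDR separately by name. State the sidedness, the effect and its scale (reconciling 0.157 with 18%), what the SD of 0.3 refers to, any correlation used, and how P and Q combine. Drop *per group*. A possible form:

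> With [n] completers, each receiving both diets ([one/two]-sided paired t-test; effect [d] on the [scale]; SD of the within-person contrast [x]; 600 metabolites, 40-80 truly different; called when P≤0.05 and Q≤0.3), average power is [a-b]% and the expected share of called metabolites that truly differ (1 - FDR) is [c-d]%.

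Then align the two paragraphs of section 7: either apply Q≤0.3 to the metabolite analysis under Statistical analysis, or remove it from Power Calculations. Reconcile 34, 30 and the section 4.1 goal of 18.

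The cost is one recalculation and protocol wording. It adds no participants, visits or assays.
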